## 4.11.1 Extent of Exposure

Descriptive summaries (mean, SD, median, min, max) will be presented for the number of vials taken and the study drug exposure by treatment group (Safety Set).

Study drug exposure will be calculated as the number of days from first to last dose date of study drug for the treatment period.

Study drug exposure (Days) = Date of last dose – Date of first dose + 1

For subjects who early withdraw, and for whom the last dose date from the End of Treatment eCRF page is unknown, the date of last available in-clinic dosing, date of withdrawal, and/or dosing recorded via the diary will be used, whichever is later.

All data for study drug exposure will be listed.

## 4.11.2 Adverse Events

All AEs that occur after the first dose of double-blind study medication to 30 days after the last dose of study medication will be considered to be treatment-emergent adverse events (TEAEs).

Where dates are missing or partially missing, adverse events will be assumed to be treatmentemergent, unless there is clear evidence (through comparison of partial dates) to suggest that the adverse event started prior to the first dose of study medication or more than 30 days after the last dose of study medication.

The MedDRA will be used to code the primary SOC and the PT of the AEs. The MedDRA version used for reporting the study will be described in relevant table and listing footnotes.

There are three categories of AE severity: Mild, Moderate and Severe. For adverse events with missing intensity, they are counted in the most conservative way as Severe in the summary by intensity.

There are five categories of AE Relationship to study treatment: Definite, Probable, Possible, Unlikely, Unrelated/Not Related. An adverse event is considered related to the study treatment if the relationship to the study treatment is considered "Definite", "Probably Related", "Probable" or 'Possible'.

All AEs and all TEAEs will be listed by subject.

All AE tables will be restricted to treatment-emergent AEs unless otherwise specified. Each subject will be counted only once within each PT or SOC. If a subject experiences more than one AE within a PT or SOC, only the AE with the strongest relationship or the worst severity, as appropriate, will be included in the summaries of relationship and severity. AEs with missing classifications regarding relationship to study treatment will be considered as related to study drug.

TEAEs will be sorted in descending order of frequency (total column) by SOC and by PT within each SOC, unless otherwise stated, alphabetical order will be used for same frequency of SOC or PT.

An overall summary of TEAEs for both the subjects with at least one AE and the total number of AEs in following categories are planned to be displayed: any TEAE, any serious TEAE, TEAE by relationship (related, not related), TEAE by severity, TEAE leading to treatment discontinuation, and any TEAEs related to a public health emergency.

The following summaries of the total number of TEAEs and the number and percentage of subjects with at least one TEAE will be provided. These will also be presented by primary SOC and PT for each treatment group:

- All TEAEs by SOC and PT
- All TEAEs by PT
- TEAEs occurring in more than 1% of study population by SOC and PT
- All TEAEs by SOC, PT and Severity
- Moderate to severe TEAEs by SOC and PT

- Drug-related TEAEs by SOC and PT
- Drug-related TEAEs by SOC, PT and Severity
- Drug-related moderate to severe TEAEs by SOC and PT
- Public health emergency related TEAEs by SOC and PT

AECOPD events as defined in the protocol will be captured as AEs with a Preferred Term of "COPD". AECOPD data will be summarized for All Exacerbations; Moderate to Severe Exacerbations; and Severe Exacerbations.

Antimuscarinic TEAEs are of interest as a common event in the LAMA drug class. The preferred terms for TEAEs considered antimuscarinic are constipation, dry mouth, dysuria, worsening of urinary retention, and worsening of narrow-angle glaucoma. The incidence of these events in this study will be presented.

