### 7.5.1 Adverse Events

Adverse events will be summarized and listed. All AEs that occur after the first dose of study medication through 30 days after the last dose will be considered to be treatment emergent AEs. The number and percentage of subjects with at least one treatment emergent AE will be presented by treatment group and events further summarized by maximum severity and relationship to study medication. Summary statistics (N, %) of AEs of special interest will be also be separately tabulated.

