### 7.5.2 Acute Exacerbations of COPD (AECOPD)

A summary of acute exacerbations of COPD reported with an AE preferred term of COPD will be descriptively summarized by severity. Exacerbation data will be summarized (N, %) for all exacerbations; moderate and severe exacerbations; and severe only exacerbations.

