#### 4.11.3 Deaths, Serious Adverse Events, and Other Significant Adverse Events

The following summaries of the total number of TEAEs and the number and percentage of subjects with at least one TEAE will be provided. These will also be presented by primary SOC and PT for each treatment group:

- All serious TEAEs by SOC and PT
- Drug-related serious TEAEs by SOC and PT
- TEAEs leading to drug discontinuation
- Serious TEAEs leading to drug discontinuation
- TEAEs leading to drug interruption
- TEAEs leading to death

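### The TEAE definition has no worsening clause, so an exacerbation that begins mild in screening and progresses on study drug could, if kept as one record, be missing from the serious, discontinuation and AECOPD tables

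*SAP*

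**What the plan says.** SAP 4.11.2 defines a TEAE by timing alone: "All AEs that occur after the first dose of double-blind study medication to 30 days after the last dose of study medication". Protocol 7.5.1 says the same: "All AEs that occur after the first dose of study medication through 30 days after the last dose". Neither mentions an event that started before the first dose and became worse after it. The SAP's rule for missing or partial dates, in the same section, asks whether the "adverse event started prior to the first dose of study medication".

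The definition controls the outputs. SAP 4.11.2 states: "All AE tables will be restricted to treatment-emergent AEs unless otherwise specified". SAP 4.11.3 lists the tables for significant events as TEAE tables, among them "All serious TEAEs by SOC and PT" and "TEAEs leading to drug discontinuation". For exacerbations, SAP 4.11.2 says that "AECOPD data will be summarized for All Exacerbations; Moderate to Severe Exacerbations; and Severe Exacerbations", and protocol 7.5.2 says that "Exacerbation data will be summarized (N, %) for all exacerbations; moderate and severe exacerbations; and severe only exacerbations". Neither of these two sentences says whether only TEAEs are counted.

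Protocol 6.4.8.1.1 requires an AECOPD to be recorded as an adverse event, and requires one that begins mild and progresses to be graded at its highest severity. Protocol 4.2.4 requires study drug to be stopped for a moderate or severe AECOPD.

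**The concern.** A definition of treatment-emergent usually has two limbs: new onset after the first dose, and worsening after the first dose of something already present. This plan has only the first. The gap matters most for AECOPD, which is a named safety endpoint and the one event type for which the protocol says how progression within a single event is graded.

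At stake is an exacerbation that becomes moderate, severe or serious while the subject is taking study drug, and that forces study drug to stop, yet is missing from the tables a reader consults for such events. The reader would have to find it in a listing. This also runs against the rest of SAP 4.11.2, which resolves doubt conservatively: unclear dates count as treatment-emergent, missing intensity as severe, missing relationship as related.

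**Working it through.** The plan states no figure to reproduce here. The check follows one subject through the plan's rules.

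1. **Recording starts before dosing.** Adverse events are collected from consent (protocol 6.1.1 and 9.1.1). Consent is at Visit 1, Day -30 to Day -4 (Table 1-1), so there is a window of 4 to 30 days in which an event can have a pre-dose onset.
2. **A mild AECOPD does not bar entry on the natural reading.** Exclusion 5 (protocol 4.2.2) and the randomization criteria (4.2.3) refer to an AECOPD needing antibiotics, systemic corticosteroids or admission. Those needs define the moderate and severe grades in 6.4.8.1.1. The mild grade needs none of them.
3. **Progression can stay within one event.** Section 6.4.8.1.1 grades a progressing exacerbation at its highest level. It does not require a new record or a new onset date, and it does not forbid one.
4. **Consequences on drug.** Moderate or severe grade requires study drug to stop (4.2.4). Severe means in-patient admission, which is normally an SAE (9.2.2).
5. **Classification.** If the site keeps one record, the start date is pre-dose. With the SAP's word for occurrence read as onset, which the missing-date rule supports, the event is not a TEAE.
6. **Outputs.**

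| Output | Is the event included? |
|---|---|
| TEAEs leading to discontinuation (SAP 4.11.3) | No |
| Serious TEAEs (SAP 4.11.3), if admitted | No |
| AECOPD summary (SAP 4.11.2) | No, under the section's default restriction to TEAEs |
| Listing of all AEs (SAP 4.11.2) | Yes |
| Disposition, early stop with reason (SAP 4.4.1) | Yes |

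7. **Do other worsening rules close the gap?** Protocol 9.2.1 makes an increase in frequency or intensity of a pre-existing condition an adverse event. Protocol 9.2.5 covers conditions present when the subject is screened. SAP 4.11.5 (Physical Findings) covers conditions found at screening. All three say what to record as an adverse event. None says that an adverse event already open at first dose becomes treatment-emergent when it worsens.

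**Size per case.** With 320 randomized, 160 per arm: 1/160 = 0.625%, about 0.6 percentage points. At the maximum of 428 there are 428/2 = 214 per arm: 1/214 = 0.467%, about 0.5 points. This is the effect of one omitted subject on one arm's incidence in each table concerned. It does not estimate how many subjects there will be, and the documents give no basis for such an estimate.

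**The case against.** The strongest reply is that the omission depends on records that cannot be seen. Section 6.4.8.1.1 is a grading rule. It sets no onset date, and a site could open a new record when the event progresses, which protocol 9.2.1 would support. How sites log such events depends on the eCRF and its completion guidelines, which the SAP mentions but which are not among the documents. This stands: a reader might infer that such an event is certain to be left out, and the documents support only the conditional statement.

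Second, the definition speaks of events occurring, and the idea of starting comes from the missing-date rule. That is fair. Onset is the better reading, but it is an inference.

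Third, the route is narrow. An AECOPD by definition calls for a change in regular medication, while LABA and ICS/LABA doses must be stable and other medication must be part of a stable regimen (protocol 5.7 and Table 5-1). Day 1 spirometry must meet every quality criterion (6.4.2). Symptoms before dosing go to the investigator (6.4.8.1), who may exclude the subject under criterion 27. Exclusion 5 can also be parsed to bar symptoms of any AECOPD. An event that later proves to need antibiotics might be logged as an eligibility deviation. All this reduces the likely number, but none of it puts the event into a safety table.

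Fourth, the event is not hidden. It is listed, the early stop is tabulated, an SAE goes to the sponsor within 24 hours (9.6.1), and the study report must give reasons for withdrawal (8.3). This also stands, and it is why the point is minor.

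A reader might also infer from the wording on all exacerbations that the AECOPD summary could count events that resolved before any study drug was given. The default restriction to TEAEs in the same section makes that reading strained.

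**Conclusion.** The definition is incomplete, and the gap is a stated rule rather than missing detail. Under it, an AECOPD that begins mild between consent and first dose and progresses on study drug would not be a TEAE. It would be missing from the TEAE-discontinuation table, from the serious-TEAE table if admitted, and by default from the AECOPD summary.

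This rests on four assumptions: occurrence means onset; a mild screening AECOPD does not bar entry; the investigator still randomizes the subject; and the site keeps a single record with its original start date.

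The point is minor. Probably very few subjects are affected, possibly none. Safety is summarized descriptively without comparison of treatments (protocol 7.5, SAP 4.11), so no test or efficacy result changes.

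A reader might go further and infer that every adverse event that starts in screening and worsens on drug is lost. The documents do not support that, because protocol 9.2.1 and 9.2.5 and SAP 4.11.5 point towards recording many such worsenings as adverse events in their own right. Those would be TEAEs if they arose after the first dose.

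**What to change.** In SAP 4.11.2:

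- Define a TEAE as an adverse event that starts after the first dose, or that starts before it and increases in severity or becomes serious after it, up to 30 days after the last dose.
- State that an AECOPD with pre-dose onset that reaches moderate or severe grade after the first dose counts in the TEAE and AECOPD tables at that grade.
- State that the AECOPD summary uses this same TEAE rule.

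Identify cases at the existing blinded data review, from AECOPD and serious adverse event records that were ongoing at first dose. Date the worsening from SAE and admission dates and from the start dates of antibiotics or systemic corticosteroids, since protocol 5.7 requires start and stop dates for concomitant medication.

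Do not add a default that treats other non-serious events ongoing at first dose as treatment-emergent when the date of worsening is unknown. The adverse event data listed in protocol 9.4 and 9.5.1 include a severity rating for each event but no date of worsening, so a single record does not show whether it worsened.

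The cost is three or four sentences, one flag in the adverse event dataset and a little blinded review, with no new data collection. Reported incidences may rise slightly. Protocol section 7 lets the SAP modify the planned analyses, and ties an amendment only to major changes to the primary endpoint or its analysis. If SAP version 2.0 is already final, SAP 4.13 provides for recording the change in the study report.

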#### 4.11.3 Deaths, Serious Adverse Events, and Other Significant Adverse Events

The following summaries of the total number of TEAEs and the number and percentage of subjects with at least one TEAE will be provided. These will also be presented by primary SOC and PT for each treatment group:

- All serious TEAEs by SOC and PT
- Drug-related serious TEAEs by SOC and PT
- TEAEs leading to drug discontinuation
- Serious TEAEs leading to drug discontinuation
- TEAEs leading to drug interruption
- TEAEs leading to death

#### 4.11.4 Clinical Laboratory Evaluation

Clinical laboratory tests will be performed at times defined in the study schedule. Any clinically significant changes in laboratory safety data should be recorded as an AE.

Hematology, chemistry and urinalysis will be collected. Laboratory data will be summarized in terms of observed values and changes from baseline and will be tabulated at each scheduled time point by treatment group and overall.

Hematology, chemistry and urinalysis data will be presented in tables as changes from baseline relative to normal ranges (e.g. shifts from normal to abnormal).

All hematology, serum chemistry and urinalysis data will be listed with values flagged if outside of the normal range.

#### 4.11.5 Vital Signs, Physical Findings and Other Observations Related to Safety

#### Vital Signs

Supine or semi-recumbent systolic blood pressure (SBP), diastolic blood pressure (DBP) and pulse rate (PR) will be measured at screening and pre-dose and 1 hour post-dose on Day 1 and 85.

SBP, DBP and pulse rate will be listed and descriptively summarized by treatment group and visit. Change from baseline values will be similarly summarized.

All data related to vital signs will be listed.

#### Physical Findings

Physical Examination, including body system of respiratory, cardiovascular, gastrointestinal, musculoskeletal, neurological system, lymph node, skin, extremities, head, ears, eyes, nose, thyroid gland, will be measured at screening and Day 85. Clinically significant conditions at Screening will be reported in the Medical History. If conditions have worsened since randomization, changes should be captured as AE/SAEs as appropriate.

Screening measurements will be listed and summarized by treatment group and visit. Shift from baseline results will be similarly summarized.

All data related to physical examination will be listed.

## Electrocardiogram

Twelve-lead ECG measurements will be measured from a single recording at screening and pre-dose and at 1 hour post-dose on Day 1 and 85.

Baseline and change from baseline for QT, QTcF, HR, QRS, RR and PR will be summarized using descriptive statistics by treatment group and visit.

For QTcF a classification of absolute values and increases from baseline will be performed. The number of subjects with maximum absolute QTcF <450 msec, 450 msec  $\leq$ QTcF <480 msec, 480 msec  $\leq$ QTcF <500 msec and QTcF values  $\geq$ 500 msec will be tabulated by treatment and visit. The number of subjects with maximum increase from baseline QTcF <30 msec, 30 msec  $\leq$ QTcF <60 msec and QTcF  $\geq$ 60 msec will be tabulated by treatment and visit.

when multiple assessments of ECG taken at a post-baseline timepoint, for the continues variables, the average of results at the same timepoint will be used, for the categorical variables, the worst ECG finding at that timepoint will be used.

All recorded values for the ECG parameters will be listed by subject. A separate listing of subjects with values of QTcF  $\geq$ 500 msec or an increase  $\geq$ 60 msec will be provided, as necessary.

## 4.12 Determination of Sample Size

The objective of this study is to confirm the efficacy of 12 weeks treatment with revefenacin 175 mcg compared with placebo administered once-daily in subjects with moderate to very severe COPD. The primary endpoint is change from baseline trough  $FEV_1$  at Day 85. The comparison of interest for the primary analysis is revefenacin 175 mcg versus placebo.

For each test on each efficacy endpoint, the null hypothesis is that there is no difference between the treatment groups.

H0: 
$$\mu_{rev} - \mu_{pbo} = 0$$

The alternative hypothesis is that there is a difference.

 $H_1: \ \mu_{rev} - \mu_{pbo} \neq 0$ 

The estimate for the difference in mean change from baseline trough  $FEV_1$  at Day 85 and the common standard deviation are based on the sample size assumptions for the revefenacin US pivotal studies (0126 and 0127) in a Western population and the GLOW7 study - a similarly designed study in a predominantly Chinese population (Wang et al., 2015).

A sample size of 256 evaluable subjects (128:128; a 1:1 ratio of revefenacin to placebo) is required to provide at least 90% power to detect a difference between revefenacin and placebo of 100 mL in the analysis of the change from baseline trough FEV1 at Day 85 assuming a standard deviation of 245 mL and a two-sided 5% significance level.

To allow for a 20% dropout rate, approximately 320 subjects in total will be randomized. In the event of a public health emergency such as COVID-19, the Sponsor may consider increasing enrollment to overcome any additional loss of information for the primary endpoint due to the inability of subjects to attend for scheduled clinic visits. The maximum number of subjects to be randomized under such circumstances will be limited to 428 (an additional 20% increase in enrollment).

## 4.13 Changes in the Conduct of the Study or Planned Analysis

A final SAP (version 1.0) will be available after the clinical protocol is approved and a Case Report Form (CRF) is available, but before the first dry run or blinded data review is performed.

The finalization of the SAP (version 2.0) will be completed prior to the database lock. Any modifications to the planned analyses after that time will be documented within the Clinical Study Report (CSR).

Wordings used in Protocol	Wordings used in SAP	Rational
Peak FEV 1 (0-2h) on Day 1	CBL to Peak FEV 1 (0-2h) on Day 85	to reflect the estimates for the analyses
SGRQ responders (total score ≥4 units) on Day 85	Number (%) of SGRQ responders (total score ≥4 units) on Day 85	to reflect the estimates for the analyses
BDI/TDI on Day 85	TDI on Day 85	BDI is measured only on Day 1
Trough $FEV_1$ on Days 29 and 57	CBL Trough FEV 1 on Days 29 and 57	to reflect the estimates for the analyses
BDI/TDI on Days 29 and 57	TDI on Days 29 and 57	BDI is measured only on Day 1

The below clarifications to the wordings of the secondary efficacy variables used in protocol (version 2.0):

Weighted Mean FEV 1 (0-2h)	CBL in Weighted Mean FEV 1	to reflect the estimates for
on Day 1 and Day 85	(0-2h) on Day 1 and Day 85	the analyses
Trough FVC on Days 29, 57	CBL Trough FVC on Days	to reflect the estimates for
and 85	29, 57, and 85	the analyses
TDI responders (focal score	Number (%) of TDI	to reflect the estimates for
$\geq$ 1) on Days 29, 57 and 85	responders (focal score $\geq 1$ ) on	the analyses
	Days 29, 57 and 85	

#### 6 Appendix

#### 6.1 Sample SAS code for MMRM

#### 6.3 Tipping-Point Multiple Imputation Method

Multiple imputation can be performed in SAS using a general three-step approach.

1) Imputation Step

The efficacy data will need to be transformed so that for each subject there is a separate column variable for the efficacy value (change from baseline  $FEV_1$ ) at each visit (e.g. SUBJID BASE CHG4 CHG8 CHG12).

PROC MI is applied to an input dataset containing some missing values, which results in creation of multiple copies of this dataset. All copies contain identical values of the non-missing data items, but different values imputed for missing items.

- a. PROC MI distinguishes two types of missingness patterns: non-monotone and monotone.
- b. In all analyses non-monotone missing data will be assumed to be missing at random

Non-monotone missing data will first be imputed using PROC MI code similar to that shown below:

Monotone missing data will then be imputed for a Tipping Point Analysis with incremental shifts (k) of +50 mL for the revefenacin arm and -50 mL for the placebo arm in 50 mL increments. This is illustrated by the example PROC MI code shown below:

2) Analysis Step

The data from the imputed datasets will then need to be transformed back prior to analysis so that for each subject at each visit a separate record is available (eg SUBJID VISIT CHG).

The following SAS code is an example of code used to summarize the primary analysis model on each of the imputed datasets:

3) Pooling Step

Results from all imputed datasets are then combined together for overall inference using PROC MIANALYZE.

The following SAS code is an example of code used to combine the individual model estimates for each imputed dataset by shift parameter:

P-values from the analyses will be presented in a two-dimensional table as illustrated in Table 7:

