## Imputing Missing Data

Missing data will only be imputed in the sensitivity analyses for the primary analysis of the primary endpoint (change from baseline trough FEV1 at Day 85). Otherwise, missing data will not be imputed.

Missing data in the primary efficacy analysis is not directly imputed and is assumed to be missing at random (MAR). In sensitivity analyses the following approaches will be used for imputing missing data:

Non-monotone missing data (e.g. subjects have missing values for intermediate visits, but have available data at subsequent visits) will be assumed to be MAR. For monotone missing data the following missing data imputation methods will be used to assess the robustness of the conclusions to the MAR assumption since it may be biased and attribute treatment benefit to withdrawals even though they are no longer taking the study treatment:

- Last-Observation-Carried Forward (LOCF) single imputation method
- Two-dimensional Tipping-point multiple imputation method

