## **Tipping-Point Analysis**

A Tipping-point analysis will be performed. Monotone missing data at all missing scheduled visits will have the value of a shift parameter (e.g. 50 mL) subtracted from the revefenacin treatment arm (worsening results) and added to the placebo arm (improving results) for change from baseline trough FEV1. The imputed datasets will then be analyzed using the MMRM primary analysis method and an estimate for the difference between the two treatments and associated 95% CI and p-value calculated. This method will be applied iteratively where at each iteration, monotone missing values are adjusted with a larger shift parameter than at the previous iteration (e.g. by 50 mL from 0 mL to -500 mL on revefenacin and 0 mL to +500 mL on placebo). This process continues until the difference between revefenacin and placebo is no longer statistically significant. This point is called the tipping point. The plausibility of the value of the shift parameters needed to change a statistically significant result (p<=0.05) to not significant (p>0.05) will be clinically assessed.

Details of tipping-point multiple imputation method are described can be found in Appendix.

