#### 4.10.1.6 Interim Analyses

Not Applicable

#### 4.10.2 Primary Efficacy Variable – CBL Trough FEV1 on Day 85

The primary efficacy variable is the change from baseline trough  $FEV_1$  on Day 85.

- Baseline FEV1 is defined as the average of the -45 and -15 minute measurements prior to dosing of study medication on Day 1 (Visit 3).
- Trough FEV1 measurements will be the pre-dose FEV1 measures on Days 29, 57 and 85 calculated as the average of the -45 and -15 minute measurements prior to dosing of study medication.
- If a public health emergency prevents FEV1 data from being measured at site then information on the reasons for the missing assessments will be recorded in the CRF

If either of the two pre-dose  $FEV_1$  measures is missing, the baseline/trough will be set to the value of the remaining non-missing measure. If both pre-dose values are missing then the baseline/trough will be set to missing.

If no baseline can be calculated for the subject, then the change from baseline values will be recorded as missing. Change in  $FEV_1$  is calculated as the Trough  $FEV_1$  – Baseline  $FEV_1$  difference such that a positive change indicates improvement.

The absolute values and the change from baseline trough FEV1 will be summarized by treatment group and visit using summary statistics for continuous data.

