## Table 7: Two-Dimensional Tipping Point Analysis Results (p-values)

			Shift P	aramete	ers for N	lissing	Data on	Revefer	nacin (m	ıL)		
		0	-50	-100	-150	-200	-250	-300	-350	-400	-450	-500
	0											
	50											
Shift	100											
Parameters	150											
for	200											
Missing	250											
Data on	300											
Placebo	350											
(mL)	400											
	450											
	500											

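### SAP Appendix 6.3 gives the tipping-point shifts with signs opposite to SAP 4.10.1.3 and Table 7; programmed as written, the check would favour revefenacin at every step

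*SAP*

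**What the plan says.** Protocol 7.3.4 plans a two-dimensional tipping-point analysis of trough FEV1 and leaves the imputation detail to the SAP. The SAP describes that analysis in three places.

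- **SAP 4.10.1.3, Tipping-Point Analysis.** The shift is "subtracted from the revefenacin treatment arm (worsening results) and added to the placebo arm (improving results"), with an example range of "0 mL to -500 mL on revefenacin and 0 mL to +500 mL on placebo" in 50 mL steps. The shift is increased until the treatment difference loses significance.
- **SAP Appendix 6.3.** The monotone missing values are imputed with "incremental shifts (k) of +50 mL for the revefenacin arm and -50 mL for the placebo arm".
- **SAP Table 7, in the same appendix.** The revefenacin columns run from 0 to -500 mL and the placebo rows from 0 to 500 mL.

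Two further statements fix the meaning of the signs. The shifted variable is the change from baseline: Appendix 6.3 says that "there is a separate column variable for the efficacy value (change from baseline" FEV1) at each visit. SAP 4.10.2 defines change as trough minus baseline, a "difference such that a positive change indicates improvement".

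**The concern.** The appendix sentence is reversed relative to the main text and to the output table it feeds. It also sits where a programmer would look, because SAP 4.10.1.3 and 4.10.2.2 both refer to the Appendix for the method.

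The SAP explains under Imputing Missing Data why it tests the missing-at-random assumption: "it may be biased and attribute treatment benefit to withdrawals even though they are no longer taking the study treatment". A tipping-point analysis answers that by making the missing active-arm values worse and the missing placebo values better until the conclusion fails. With the signs reversed it does the opposite, and adds the very benefit it is meant to take away. Every cell of the table would then stay significant, and the result could be reported as robust to any departure from missing at random when nothing had been tested. LOCF is the other imputation-based sensitivity analysis, but it applies no shift and does not fill the gap.

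**Working it through.** **1. Signs side by side**

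| Source | Revefenacin | Placebo | Effect on difference (revefenacin minus placebo) |
|---|---|---|---|
| SAP 4.10.1.3 | 0 to -500 mL | 0 to +500 mL | falls |
| SAP Table 7 | 0 to -500 mL | 0 to 500 mL | falls |
| SAP Appendix 6.3 | +50 mL steps | -50 mL steps | rises |

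**2. Inputs.** From SAP 4.12: difference 100 mL, SD 245 mL, two-sided 5%, 256 evaluable, 20% dropout, about 320 randomized (160 per arm). From Protocol 2.2: pooled earlier result 148.13 mL. Assumed, because the documents do not give them: the fraction *m* of monotone-missing Day 85 values (5 to 30%), equal in the two arms; the same shift *k* in both arms; and the shift applied directly to the imputed Day 85 values.

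**3. The plan's own figure.** n per arm = 2 × (245/100)² × (1.960 + 1.282)² = 126.1, so 127 by the normal approximation. With 128 per arm, power is 90.4% (normal) or 90.2% (t-test). 256/0.8 = 320. The stated sample size is reproduced.

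**4. Formulas**

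- Intended signs: d = D - 2mk
- Appendix 6.3 signs: d = D + 2mk
- Both: SE² = 2 × [245²/(160(1 - m)) + m(1 - m)k²/160]

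Example with D = 100, m = 0.20, k = 100: SE² = 2 × [60025/128 + 0.16 × 10000/160] = 2 × (468.9 + 10) = 957.9, so SE = 30.9. Intended signs: d = 60, z = 1.94, p = 0.053. Appendix signs: d = 140, z = 4.52.

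**5. D = 100 mL, 20% missing per arm, step by step**

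| k (mL) | Intended: d, p | Appendix 6.3: d, z |
|---|---|---|
| 0 | 100, 0.0011 | 100, 3.27 |
| 50 | 80, 0.009 | 120, 3.91 |
| 100 | 60, 0.053 (tips) | 140, 4.52 |
| 250 | 0, 1.00 | 200, 6.13 |
| 500 | already tipped at 100 | 300, 7.91 |

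**6. Other missing fractions.** First 50 mL step at which p exceeds 0.05 under the intended signs, and the difference reached at k = 500 under the appendix signs:

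| m | D = 100: tips at | D = 148.13: tips at | D = 100, appendix signs, d at k = 500 |
|---|---|---|---|
| 5% | 450 mL (p = 0.068) | 850 mL, off the grid | 150 mL |
| 10% | 250 mL (p = 0.096) | 450 mL (p = 0.074) | 200 mL |
| 20% | 100 mL (p = 0.053) | 250 mL (p = 0.140) | 300 mL |
| 30% | 100 mL (p = 0.227) | 150 mL (p = 0.084) | 400 mL |

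Under the appendix signs z rose at every step to 500 mL for differences of 60, 100 and 148 mL at all four fractions, even though the SE also grows with k.

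**7. Simulation.** Three visits, assumed correlation 0.7, 20 imputations, 200 trials in each of the eight scenarios. Median tipping points under the intended signs matched the table, except 150 mL instead of 100 mL for D = 100 at 20% missing. Under the appendix signs, 0 of 1,544 significant trials tipped.

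**The case against.** The strongest counter-argument is that the intended direction is not in doubt. SAP 4.10.1.3 gives it in words, as a numerical range and through its stopping rule. Table 7 has no positive revefenacin column and no negative placebo row, so reversed shifts could not be reported under its labels. SAP 4.1 requires independent checking of outputs. The example code that the appendix refers to is not in the supplied text, and it may subtract k, which would make the sentence harmless. All this stands, and it is why the consequence is stated conditionally. It shows what was meant, not what was programmed, and the sentence at fault is in the section that specifies the method.

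A second objection concerns the numbers. The tipping points under the intended signs describe the correct analysis, not the error, and rest on assumed missing fractions. That is fair: they serve only to show that the intended check can tip within the grid. Early-termination spirometry is mapped to analysis visits (SAP 4.3.3), so Day 85 missingness could be below 20%. Also, SAP 4.10.1.3 shifts every missing scheduled visit. If the code carries shifted values into later imputations, then at correlation 0.7 a subject missing both Days 57 and 85 has an effective Day 85 shift of k(1 + 0.7/1.7) = 1.41k. The tipping points would then be lower than tabulated. The direction is the same either way.

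**Conclusion.** The concern holds. The Appendix 6.3 sentence contradicts SAP 4.10.1.3 and Table 7 and is wrong as written. If the program follows it, each joint 50 mL step moves the difference by 100 × m mL in favour of revefenacin (5, 10, 20 or 30 mL at 5, 10, 20 or 30% missing) instead of against it, and a significant result for revefenacin cannot be overturned. The direction needs no assumption beyond some monotone-missing data; the sizes rest on equal missingness and equal shifts in the two arms and on the planning SD.

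The effect is confined to this sensitivity analysis. It should be fixed, because the analysis is the SAP's only delta-adjusted test of missing at random for the primary endpoint. The contradiction in the text is certain; whether the code carries it cannot be judged from the documents.

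**What to change.** - In SAP Appendix 6.3, change the sentence to increments of -50 mL for revefenacin and +50 mL for placebo, matching SAP 4.10.1.3 and Table 7.
- Before unblinding, confirm the sign of the shift in both the example and the production PROC MI code.
- Test the program on dummy treatment codes. Moving away from the 0/0 cell of Table 7 must lower the pooled difference. If 20% per arm are missing and each missing Day 85 value is shifted by exactly k, the fall at the -100/+100 cell is 2 × 0.20 × 100 = 40 mL. If shifted values feed later imputations it will be larger: about 56 mL if all of them miss both Days 57 and 85, at correlation 0.7. The pass criterion should therefore be the direction.
- If the database is already locked, record the correction in the clinical study report, as SAP 4.13 provides.

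The cost is one line of text and one program check. The primary analysis does not change.
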